8.2.3 Expectedness

The PI will be responsible for determining whether an AE is expected or unexpected. An AE will be considered unexpected if the nature, severity, or frequency of the event is not consistent with the risk information described in the current IB for IFx-Hu 2.0.

8.3 Time Period and Frequency of Event Assessment and Follow-up

The occurrence of an AE or SAE may come to the attention of study personnel during study visits and interviews of a study participant presenting for medical care, or upon review by a study monitor. All AEs including local and systemic reactions not meeting the criteria for SAEs will be captured on the appropriate CRF. Information to be collected includes an event description, time of onset, clinician's assessment of severity, relationship to study product (assessed only by those with the training and authority to make a diagnosis), and time of resolution/stabilization of the event. All AEs occurring during the study must be documented appropriately regardless of relationship. All AEs will be followed to adequate resolution.

Any medical condition that is present at the time the participant is screened will be considered as baseline and not reported as an AE. However, if the study participant's condition deteriorates at any time during the study, it will be recorded as an AE. UPs will be recorded in the data collection system throughout the study.

Changes in the severity of an AE will be documented to allow an assessment of the duration of the event at each level of severity to be performed. AEs characterized as intermittent require documentation of onset and duration of each episode.

The PI will record all reportable events with start dates occurring any time after informed consent is obtained. At each study visit, the investigator will inquire about the occurrence of AE/SAEs since the last visit. Events will be followed for outcome information until resolution or stabilization.

8.4 Reporting Procedures

8.4.1 Adverse Event Reporting

All adverse events will be documented and reported to the FDA in the annual report.

8.4.3 Unexpected Adverse Drug Experience Problem Reporting

Incidents or events that meet the FDA criteria for UPs require the creation and completion of a UP report form. It is the site investigator's responsibility to report UPs to their IRB and to the study sponsor. The UP report will include the following information:

- Protocol identifying information: protocol title and number, PI's name, and the IRB project number
- A detailed description of the event, incident, experience, or outcome
- An explanation of the basis for determining that the event, incident, experience, or outcome represents a UP
- A description of any changes to the protocol or other corrective actions that have been taken or are proposed in response to the UP.

To satisfy the requirement for prompt reporting, UPs will be reported using the following timeline:

- UPs that are SAEs will be reported to the IRB and to the study sponsor within 24 hours of the investigator becoming aware of the event.
- Any other UP will be reported to the IRB and to the study sponsor within 7 business days of the investigator becoming aware of the problem.

8.4.4 Reporting of Pregnancy

All women of childbearing potential should be instructed to contact the investigator immediately if they suspect they might be pregnant (e.g., missed or late menstrual period) at any time during study participation.

8.5 Study Halting Rules

Administration of study agent will be halted when two grade-3 or greater AEs determined to be "possibly" or "probably" related are reported. The clinical team will notify the PI, the Peachtree Bioresearch Solutions, Inc. (PBRS) Medical Monitor (MM), and the Sponsor's designated Drug Safety Unit immediately when a second grade 3 event is reported, and the site will stop accepting new study participants. The PI will inform the PBRS MM and the Sponsor's designated Drug Safety Unit within 24 hours of this occurrence and will provide both with AE listing reports. The PBRS MM will provide

recommendations for proceeding with the study to the clinical team and study sponsor. The study sponsor will inform the FDA of the temporary halt and the disposition of the study.

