The trial will be conducted in accordance with the ICH E6, the Code of Federal Regulations on the Protection of Human Subjects (45 CFR Part 46). The Principal Investigator will assure that no deviation from, or changes to the protocol will take place without prior agreement from the sponsor and documented approval from the Institutional Review Board (IRB), except where necessary to eliminate an immediate hazard(s) to the trial participants. All personnel involved in the conduct of this study have completed Human Subjects Protection Training.

I agree to ensure that all staff members involved in the conduct of this study are informed about their obligations in meeting the above commitments.

Principal Investigator: _____

[figure not shown]
Signature: _____ Date: _____

PROTOCOL SUMMARY

Title	Phase 1 Study Using a Plasmid DNA Coding for Emm55 Streptococcal Antigen in Patients with Unresectable Stage III or Stage IV Cutaneous Melanoma
Short Title	pDNA Intralesional Cancer Vaccine for Cutaneous Melanoma
Protocol Number	Melanoma 2017-01
Phase	Phase 1
Methodology	Non-randomized, open-label, uncontrolled
Study Duration	Approximately 1 year
Study Center(s)	Single-center
Objectives	Primary: To assess safety and feasibility Secondary: To assess any antitumor response
Number of Subjects	Six
Diagnosis and Main Inclusion Criteria	Male or female, confirmed stage III or stage IV unresectable melanoma with lesions accessible for intralesional injection
Study Product, Dose, Route, Regimen	Plasmid DNA encoding a Streptococcal antigen in a cationic polymer-based solution in doses of 100 µg delivered intralesionally at a single time point “Week 0” with a maximum of three lesions injected. The primary endpoint (DLT) will be assessed at 4 weeks.
Optional dosing	After primary endpoint has been met (DLT), at the investigator’s discretion in consultation with the sponsor, patients may receive additional doses on a 3-week cycle.
Follow-up - Primary	Week 4; Day 28+/-7 business days.
Follow-up – Optional.	21 days +/- 7 business days from last dose administered.
Follow-up – Long-term	Obtain OS/subsequent treatments for melanoma after MCC 19500 as of 11/16/2020 for all patients with clinical response if available.

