Enrollees will receive IFx-Hu2.0 at a single time point. Depending on the number of accessible lesions, a patient could receive up to three doses across three lesions (one dose per lesion). Forty milliliters of peripheral blood will be collected from these patients prior to treatment administration and at the follow-up visit four weeks later. The target dose will be 100 µg of plasmid DNA per lesion injected at a final dose volume of 200 µL per lesion. To allow for the observation of any acute toxicity in the first subject enrolled and prevent any occurrence of excessive toxicities in subsequent subjects, the first subject enrolled will receive a single dose of IFx-Hu2.0. Subsequent subjects will be administered the product after at least seven days. Beyond the first subject, the maximum number of lesions to be injected at any given time point in the study phase proposed is three lesions. These samples will be used to perform complete blood counts (CBC) and clinical chemistry tests. A urine sample will be obtained for urinalysis for protein and blood at the same frequency. Blood samples will be drawn for immune response evaluation as well. Peripheral blood collections, and where feasible, as determined by PI, tumor biopsies may be obtained on the first and subsequent treatment cycles. At the end of the study period a biopsy of the lesion injected and a non-injected lesion (if applicable) will be collected. At the discretion of the PI in consultation with the Sponsor, the patient will have the option of continuing the study at three-week intervals so long as the subject under study has not progressed.

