4.2 Study Endpoints

4.2.1 Primary Endpoint

The primary endpoints of this trial will be the safety and feasibility of the treatment regimen. Safety will be reported using Common Terminology Criteria for Adverse Events (CTCAE) version 5.0. Feasibility will be defined as the ability to treat at least five of the six patients enrolled without dose-limiting toxicity (DLT).

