7.3.7 Schedule of Events Table

Schedule of Events Table

Schedule of Events: (Single dose cycle scenario)

Procedure	Screening (Day -36 to -1)	Week 0 (D=0)	Week 4** (D=28)*	Unscheduled visit	Early Termination Visit	Long-term Follow-up ¹
Informed consent eligibility	X					X
Physical exam w/vitals	X	X	X	X	X	
Medical history	X			X	X	X
Concomitant meds.	X	X	X	X	X	
AEs/SAEs	X	X	X	X	X	
IFx-Hu2.0 dosing		X				
Blood for Immune Response Evaluation		X	X	X	X	
***Clinical labs						
CBC, CMP	X	X	X	X	X	
LDH	X	X	X	X	X	
Blood clotting tests (PT/PTT)	X		X		X	
HLA typing (if not previously reported)		X				
EBV ab	X					
Hepatitis B and C, HTLV-1 & 2	X					
HIV, RPR (FTA if necessary)	X					
Thyroid Tests (Free T4, TSH)	X		X		X	
Serum Pregnancy Test	X	X	X		X	
Immunodeficiency Panel	X					
Urinalysis	X	X	X	X	X	
Anti-double-stranded DNA (anti-dsDNA)	X		X		X	
Anti-DNAse B Titer Serum	X		X		X	

ECG	X					
Optional Tumor sample/biopsies for immune response assays	X	X	X	X	X	
Optional Tumor sample/biopsies for histology	X		X	X	X	
CT and/or PET scan (Photographs may be utilized for melanoma confined to the skin)	X		X		X	
Performance Status	X	X	X	X	X	
Tumor Burden (lesion measurements)	X	X	X	X	X	
Confirmation of histology by Moffitt (may use archival tissue)	X					
Overall Survival						X

* +/-7 business days; **Final study visit; ***Screening labs may be performed within 7 days of treatment.

¹A long-term follow-up on 11/16/2020 (\pm 4 weeks) that includes the survival status and subsequent anti-cancer therapy since last being seen on trial will be obtained from the EMR. Subsequent therapies will be documented from the EMR for melanoma (immune-based therapy, chemotherapy, radiation, surgery) with clinical response if available.

Schedule of Events: (optional multiple dose cycle scenario, sample schedule for 3 cycles)

Procedure	Screening (Day -36 to -1)	Week 0 (D=0)	Week 4 (D=28)*	Week 7 (D=49)*	visit (21 days after last dose)	Unscheduled Visit	Early Term Visit	Long-term Follow-up ¹
Informed consent Eligibility	X							X
Physical exam w/vitals	X	X	X	X	X	X	X	
Medical history	X					X	X	X
Concomitant meds.	X	X	X	X	X	X	X	
AEs/SAEs	X	X	X	X	X	X	X	
IFx-Hu2.0 dosing		X	X	X				
Blood for Immune Response Evaluation		X	X	X	X	X	X	
***Clinical labs								
CBC, CMP	X	X	X	X	X	X	X	
LDH	X	X	X	X	X	X	X	
Blood clotting tests (PT/PTT)	X		X		X		X	
HLA typing (if not previously reported)	X							
EBV ab	X							
Hepatitis B and C, HTLV-1 & 2	X							
HIV, RPR (FTA if necessary)	X							

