10.5 Sample Size

The intent of this study is to enroll six evaluable patients to assess the safety of IFx-Hu2.0 as a monotherapy. The sample size has the following precision for estimation of DLT rates for estimating ranging from 0.1 to 0.5. A DLT is defined as an adverse event equal to or greater than grade 3, definitely related to the investigational agent within a 4 week period. Precision is measured by 1-sided 95% upper confidence limit on the estimated DLT rate via exact binomial distribution. For example, if no DLT is observed in patients on IFX-Hu 2.0, then the true underlying DLT rate is lower than 0.393 with 95% confidence.

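### The mandatory dosing halt in 8.5 does not count definitely related events, the only ones that can be DLTs, and one related grade 3 or greater event in subject 1 triggers no predefined hold

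*Combined protocol and SAP*

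**What the plan says.** **The halt.** Section 8.5: "Administration of study agent will be halted when two grade-3 or greater AEs determined to be" *possibly* or *probably* related are reported. The next sentence requires immediate notification and an end to accrual once a second grade 3 event is reported, and sets no limit on relatedness. The Medical Monitor then recommends how to proceed.

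**Relatedness and DLTs.** Section 8.2.2 has five categories, and *definitely related* is separate from *probably* and *possibly related*. Section 10.5: "A DLT is defined as an adverse event equal to or greater than grade 3, definitely related to the investigational agent", within four weeks. Section 4.2.1: "Feasibility will be defined as the ability to treat at least five of the six patients enrolled" without a DLT.

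**The first-subject step.** Section 4.1 gives subject 1 one dose, to observe acute toxicity and "prevent any occurrence of excessive toxicities in subsequent subjects". The release condition is: "Subsequent subjects will be administered the product after at least seven days". Later subjects may have up to three lesions injected at one visit.

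**When AEs are checked.** Section 8.3: "At each study visit, the investigator will inquire about the occurrence of AE/SAEs since the last visit". The Protocol Summary and 7.3.2 plan observation for immediate reactions on Day 0. The next planned visit in 7.3.7 is "Week 4; Day 28+/-7 business days" (Protocol Summary, primary follow-up). Unscheduled visits are allowed but not planned.

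**Other safeguards.** Section 5.5 allows suspension on safety grounds. Section 8.1.2 makes grade 4 and 5 events serious, except myelosuppression that needs no hospital admission. Section 8.4.2 sends SAEs to the sponsor within 24 hours, and 8.4.3 sets deadlines for unexpected events. Section 8.6 provides ongoing Medical Monitor review, and 15.1 continuous monitoring by the PI.

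**The concern.** A halting rule should respond at least as strongly to a clearly drug-caused event as to a doubtful one. As worded, 8.5 counts the doubtful events and not the certain ones. Stopping accrual does not replace a dosing halt. Screening can begin 36 days before dosing, so enrolled subjects may be waiting for a first dose, and 6.1.9 allows repeat doses on a 3-week cycle. Neither group is covered by a rule that only closes the study to new participants.

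The first-subject step has a related weakness. Its stated purpose is to protect later subjects, who may receive three times subject 1's dose at one visit, but the only condition for releasing them is elapsed time. If subject 1 has one related grade 3 or greater event after leaving the clinic on Day 0, no text requires anyone to look for it before subject 2 is dosed, or to wait once it is known.

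**Working it through.** **1. The plan's own figure.** Section 10.5 gives 0.393 as the one-sided 95% exact upper limit for 0 DLTs in 6 patients. Check: 1 − 0.05^(1/6) = 0.3930, which agrees. The section's range of DLT rates, 0.1 to 0.5, supplies the illustrative rates in step 4.

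**2. Which events count, for grade 3 or greater AEs.**

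| Relatedness (8.2.2) | Counts towards the dosing halt (8.5, first sentence) | Can be a DLT (10.5) |
|---|---|---|
| Definitely | No, not named | Yes, if within 4 weeks |
| Probably | Yes | No |
| Possibly | Yes | No |
| Unlikely, Not related | No | No |

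Read literally, the two sets do not overlap. If two patients have DLTs, 6 − 2 = 4 patients are DLT-free, below the five required, yet the halt count is 0. One definitely and one possibly related event give a count of 1, which is also no halt. If both are grade 3 events, the second sentence of 8.5 stops accrual and triggers notification.

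**3. Timing.** Assume weekday dosing and no holidays. Day 28 falls on the same weekday as Day 0.
- Minus 7 business days: Day 17 for Monday or Tuesday dosing, Day 19 for Wednesday to Friday.
- Plus 7 business days: Day 37 for Monday to Wednesday, Day 39 for Thursday or Friday.
- Subject 2 can be dosed from Day 7, so at least 17 − 7 = 10 days before subject 1's next planned AE inquiry.
- If every subject follows the previous one by seven days (Days 0, 7, 14, 21, 28, 35), three subjects, including subject 1, have been dosed before Day 17 or 19, four before Day 28, and all six before Day 37.
- If the seven days apply only after subject 1, which 4.1 leaves open, all five others could be dosed from Day 7.

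**4. Illustration of exposure.** The documents give no rate for related grade 3 or greater AEs, so p per patient is assumed. Further assumptions: at most one such AE per patient, independence between patients, every event rated possibly or probably related, and no discretionary suspension. The low end supposes that each outcome is known before the next dose. The high end supposes that subjects 2 to 6 are all dosed before any of their outcomes is known.
- Further subjects dosed, given an event in subject 1: (1 − (1−p)^5)/p, up to 5.
- Further subjects dosed, unconditionally: 1 − (1−p)^5, up to 5p.
- Further subjects affected, unconditionally: p(1 − (1−p)^5), up to 5p².
- Chance that no second event occurs, given one in subject 1: (1−p)^5.

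| p | Dosed, given event | Dosed, unconditional | Affected, unconditional | No second event, given one |
|---|---|---|---|---|
| 0.1 | 4.10 to 5 | 0.41 to 0.50 | 0.04 to 0.05 | 0.590 |
| 0.2 | 3.36 to 5 | 0.67 to 1.00 | 0.13 to 0.20 | 0.328 |
| 0.5 (stress case) | 1.94 to 5 | 0.97 to 2.50 | 0.48 to 1.25 | 0.031 |

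For example, at p = 0.2: 0.8^5 = 0.328, (1 − 0.328)/0.2 = 3.36, and 0.2 × 0.672 = 0.13.

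**5. Reporting time for a non-serious event.** Under 8.4.3, an unexpected event that is not an SAE may reach the sponsor up to 7 business days after awareness. That is at most 9 calendar days (awareness Monday to Wednesday) or 11 (Thursday or Friday), longer than the seven-day interval. It is a limit on reporting to the sponsor, not a delay in the site's own awareness.

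**The case against.** The best defence is that this is one site with six patients, monitored continuously by the PI. A related grade 4 or 5 event is almost always serious under 8.1.2 and reaches the sponsor within 24 hours, and 5.5 gives clear grounds to suspend. A two-event threshold also fits a feasibility criterion that tolerates one DLT in six. The missing word is probably a drafting slip, since nobody would intend to halt for possible relatedness and continue for definite. The animal experience in 2.3.2, with no adverse events in more than 200 animals, makes high event rates look unlikely. Most of this stands. It lowers the practical risk, but it does not supply a rule: none of these provisions requires a hold or is tied to releasing subject 2.

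A reader might infer more than the text supports:
- *That subject 1 has no AE check before subject 2 is dosed.* Immediate reactions are observed on Day 0, and acute toxicity is what 4.1 says the step is for. The gap runs from that observation to Week 4.
- *That definitely related events trigger nothing in 8.5.* A second grade 3 event of any relatedness stops accrual and triggers notification.
- *That dosing would continue after a related death.* No rule forbids it, but it would need the PI, sponsor, Medical Monitor and IRB all to decline to act.
- *That two events means two patients.* Section 8.5 counts AEs, so two qualifying AEs in subject 1 already meet it.

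**Conclusion.** The halting rule is wrong as written: taken literally, the events that define a DLT cannot trigger the dosing halt. This rests on the text alone. So does the second finding, that one related grade 3 or greater event in subject 1 leads to no predefined hold and that subject 2 is released by elapsed time, 10 days or more before the next planned AE inquiry.

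In practice the gap is mainly a single non-serious grade 3 event in subject 1, because serious events have fast reporting and a discretionary hold is likely. The exposure figures show only what the written rules permit under assumed rates. They are neither a forecast nor the benefit of the fix, since dosing may resume after review. At p = 0.1 the unconditional effect is small, about 0.04 to 0.05 further subjects affected. The case for change is that the rule misses its purpose and is easy to correct.

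**What to change.** 1. In 8.5, change the trigger to *possibly, probably or definitely related*, and state that a single related grade 5 event halts dosing pending Medical Monitor review.
2. In 4.1, release subject 2 only after the site has recorded subject 1's AE status at or after Day 7, by phone or chart, and found no related grade 3 or greater AE. If such an event in subject 1 is reported at any time in the 4-week DLT window, hold dosing of all subjects not yet dosed until the Medical Monitor's recommendation is recorded.

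This is a hold for review, not a stop, so it remains compatible with tolerating one DLT in six. It cannot protect subject 2 from an event in subject 1 that is found only after subject 2 has been dosed, but the hold then covers those still waiting. Section 8.6 needs no change, because 8.5 already has the Medical Monitor recommend how to proceed. The cost is a short amendment to two sections, one phone or chart check by existing staff, and a possible short delay.

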6.1.9 Duration of Therapy

Participants enrolled in the study will receive IFx-Hu2.0 at a single time point. After primary endpoint has been met (DLT), at the investigator's discretion in consultation with the sponsor, patients may receive additional doses on a 3-week cycle.

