7.3.2 Enrollment /Baseline

Enrollment/Baseline Visit (Visit 1, Day 0)

- Obtain demographic information, medical history, medication history, alcohol and tobacco use history.
- Record Concomitant Medications.
- Record vital signs, results of physical examination, other assessments.
- Collect blood/urine for:
 - Hematology: CBC - hemoglobin, hematocrit, white blood cells (WBC) with differential count, platelet count
 - Biochemistry: CMP - glucose, calcium, albumin, total protein, sodium, potassium, CO₂, chloride, BUN, creatinine, total bilirubin, alanine aminotransferase (ALT), aspartate aminotransferase (AST), alkaline phosphatase (ALP), lactate dehydrogenase (LDH)
 - Urinalysis: UA with microscopic evaluation
 - Serum pregnancy test: done within 24 hours prior to Investigational Product administration, and results must be available prior to Investigational Product administration
 - 40 mL of blood will be collected for research purposes in the laboratory of [name], including immune response baseline evaluation.
- Where feasible, as determined by PI, research study biopsy for histology and/or immune response assays may be collected at the screening visit or the baseline visit.
- Administer the Investigational Product.
- Assessment and recording of ECOG Performance Status
- Assessment and recording of Tumor Burden (lesion measurements)
- Observation and recording of adverse or serious adverse events as defined by CTCAE v5.0

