8.2.2 Relationship to Study Event

The clinician’s assessment of an AE’s relationship to IFx-Hu2.0 is part of the documentation process, but it is not a factor in determining what is or is not reported in the study. If there is any doubt as to whether a clinical observation is an AE, the event should be reported. All AEs must have their relationship to study agent assessed. To help assess, the following guidelines are used.

- **Definitely Related** – There is clear evidence to suggest a causal relationship, and other possible contributing factors can be ruled out. The clinical event, including an abnormal laboratory test result, occurs in a plausible time relationship to study intervention administration and cannot be explained by concurrent disease or other drugs or chemicals. The response to withdrawal of the study intervention (dechallenge) should be clinically plausible. The event must be pharmacologically definitive, with use of a satisfactory rechallenge procedure if necessary.
- **Probably Related** – There is evidence to suggest a causal relationship, and the influence of other factors is unlikely. The clinical event, including an abnormal laboratory test result, occurs within a reasonable time after administration of the study intervention, is unlikely to be attributed to concurrent disease or other drugs or chemicals, and follows a clinically reasonable response on withdrawal (dechallenge). Rechallenge information is not required to fulfill this definition.
- **Possibly Related** – There is some evidence to suggest a causal relationship (e.g., the event occurred within a reasonable time after administration of the trial medication). However, other factors may have contributed to the event (e.g., the participant’s clinical condition, other concomitant events). Although an AE may rate only as “possibly related” soon after discovery, it can be flagged as requiring more information and later be upgraded to “probably related” or “definitely related”, as appropriate.

- **Unlikely to be related** – A clinical event, including an abnormal laboratory test result, whose temporal relationship to study intervention administration makes a causal relationship improbable (e.g., the event did not occur within a reasonable time after administration of the study intervention) and in which other drugs or chemicals or underlying disease provides plausible explanations (e.g., the participant's clinical condition, other concomitant treatments).

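### The dosing halt in 8.5 omits definitely related events, so dose-limiting toxicities add 0 to its count

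*Combined protocol and SAP*

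**What the plan says.** All references are to the combined protocol and SAP.

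- **Dosing halt (8.5, first sentence).** Administration stops when "two grade-3 or greater AEs determined to be 'possibly' or 'probably' related are reported". This is the only rule in the plan that halts dosing on a count of events.
- **Notification and accrual stop (8.5, second sentence).** The investigator, the medical monitor and the sponsor's safety unit are told "immediately when a second grade 3 event is reported, and the site will stop accepting new study participants". No attribution is given here, and the grade is stated as 3, not as 3 or greater.
- **Attribution scale (8.2.2).** There are five categories: definitely, probably, possibly, unlikely and not related. The top one has its own criteria, starting with "There is clear evidence to suggest a causal relationship, and other possible contributing factors can be ruled out".
- **DLT (10.5).** A DLT is an adverse event of grade 3 or more, "definitely related to the investigational agent within a 4 week period".
- **Feasibility (4.2.1 and 10.4.1).** At least five of the six patients must be treated without a DLT.
- **Further dosing (6.1.9).** Once the DLT primary endpoint has been met, at the investigator's "discretion in consultation with the sponsor, patients may receive additional doses on a 3-week cycle". Section 4.1 allows continuation "at three-week intervals so long as the subject under study has not progressed", and 7.1.2 offers it to patients who respond. Section 6.1.8 provides for no dose modification.

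**The concern.** A halting rule should respond at least as strongly to events that are surely caused by the drug as to events that only may be. Here the two lower related categories count and the highest does not. The omitted category is also the one that defines a DLT. Taken literally, the trial's own dose-limiting events cannot trigger its dosing halt, and two events rated only possibly related can.

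What is at stake is the automatic part of the safety oversight in a Phase 1 trial whose primary objective is safety. After two definitely related severe events, the written count does not stop dosing. Any further injection in enrolled patients then rests on judgement, not on a rule set in advance.

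**Working it through.** **1. The plan's own figure.** Section 10.5 gives a one-sided 95% exact upper limit of 0.393 for 0 DLTs in 6 patients. The formula is 1 − 0.05^(1/6) = 0.3930, so the figure reproduces. It depends on the DLT definition and the sample size, not on 8.5, and this point does not affect it.

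**2. Overlap of the two definitions.** The labels that count toward the dosing halt are {possibly, probably}. The label that makes a DLT is {definitely}. They have no label in common, so each DLT adds 0 to the halt count.

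**3. Every pair of related events of grade 3 or greater (halt needs a count of 2).**

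| Pair | Count as written | Halt? | Count with definitely added |
|---|---|---|---|
| definitely + definitely | 0 | no | 2 |
| definitely + probably | 1 | no | 2 |
| definitely + possibly | 1 | no | 2 |
| probably + probably | 2 | yes | 2 |
| probably + possibly | 2 | yes | 2 |
| possibly + possibly | 2 | yes | 2 |

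As written, 3 of the 6 pairs halt dosing; with the category added, all 6 do. These are label combinations, not probabilities.

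**4. Against the feasibility criterion.** Two patients with a DLT leave 6 − 2 = 4 without one. The criterion needs 5, so feasibility fails while those DLTs contribute 0 to the halt.

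**5. How often two or more patients would have a DLT.** Section 10.5 considers true DLT rates p from 0.1 to 0.5. Assuming six independent patients, all treated, the chance of two or more with a DLT is 1 − (1 − p)^6 − 6p(1 − p)^5. This is 0.114, 0.345, 0.580, 0.767 and 0.891 at p = 0.1, 0.2, 0.3, 0.4 and 0.5. These values show that the situation is not remote within the plan's own range. They are not the chance of a missed halt, because other events may trigger the rule.

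**6. Which doses are exposed.**

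- *Enrolled patients without a DLT of their own.* The stated conditions for continuing are no progression (4.1), response (7.1.2) and the DLT gate in 6.1.9. If that gate is applied patient by patient, DLTs in two other patients do not close it. The schedule supports this reading: the Protocol Summary has the DLT endpoint assessed at 4 weeks, and the sample schedule in 7.3.7 re-doses at Week 4. Section 4.1 delays later subjects by at least seven days after the first. On nominal days the second subject therefore completes four weeks no earlier than day 7 + 28 = 35, after the first subject's Week 4 visit on day 28. A gate that waited for the study-wide result could not be passed at that visit.
- *A patient who has had a DLT.* If the gate means passing four weeks without a DLT, this patient is barred. If it only means that the four-week assessment has been done, the patient is not. The wording of 6.1.9 does not settle this.
- *New participants.* The first dose is given at the Day 0 enrollment visit (7.3.2), so an accrual stop would also stop first doses. The second sentence of 8.5 achieves this only if its second grade 3 event covers any attribution and includes grades 4 and 5. The text states neither.

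**7. Amount of dosing left to judgement.** The sample schedule doses at Weeks 0, 4 and 7, which gives 2 optional visits. With 1 to 3 lesions per visit at 100 µg each (6.1.5), full uptake means 2 × 1 = 2 injections (200 µg) to 2 × 3 = 6 injections (600 µg) per patient. The minimum is 0, if optional dosing is not taken up or is already finished. The maximum assumes that both events come before any optional dose. The schedule is labelled a sample, so 600 µg is not a cap.

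**The case against.** The strongest reply is that no clinician would ignore two definitely related severe events. On a purposive reading, the first sentence of 8.5 sets a minimum level of attribution that a definite event exceeds. That is very likely the intent, and it is why this looks like a drafting slip. But nothing in the document says at least possibly related, and a halting rule should not need inference about the label that defines the trial's DLT.

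A second reply is that 6.1.9 opens further dosing only once the DLT endpoint has been met, and that feasibility is one of the primary endpoints. With two DLTs the gate would then be shut for everyone. The wording allows this, but the Week 4 re-dosing in the sample schedule fits it poorly. What stands is that the gate may well bar a patient who has had a DLT. A reader might infer that such a patient would be re-dosed freely; the text does not establish that.

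A third reply is that the definite-plus-definite case is narrow. Section 8.2.2 sets a demanding standard, and an event first reported as possibly or probably related counts when reported. This limits how often the gap matters and does not close it.

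Finally, other safeguards exist. With a stated exception for myelosuppression, grade 4 and 5 events are serious by definition (8.1.2). Serious events reach the sponsor within 24 hours (8.4.2), and unexpected ones also go to the IRB (8.4.3). The investigator may withdraw a patient (5.4.1), the study may be suspended (5.5) and the medical monitor reviews safety continually (8.6). All of this stands and lowers the practical risk. It prompts review; none of it halts dosing automatically.

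**Conclusion.** The dosing-halt trigger in 8.5 is wrong as written, probably through a slip. Two DLTs add 0 to a count that needs 2, and one definite event paired with a lesser-attributed one adds 1, although two DLT patients already fail feasibility at 4 of 6. This follows directly from 8.5, 8.2.2 and 10.5.

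The scope is less certain. The clearest exposure is optional re-dosing of enrolled patients who have had no DLT themselves, assuming that the gate in 6.1.9 works patient by patient. On the sample schedule this is 0 to 6 injections per patient.

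Two opposite inferences about new participants go too far: that they are fully protected by the accrual stop, and that they are fully exposed. Either depends on how the second sentence of 8.5 is read. It would also be wrong to infer that severe related events would go unreviewed, or that the trial's estimates are compromised. Reporting and discretionary oversight remain in place, and no estimate, endpoint or sample size changes. The point deserves correction because the rule is a safety rule and the remedy is nearly free.

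**What to change.** Amend 8.5 in two places:

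1. In the first sentence, add definitely to the attributions that count, so that dosing halts on two events of grade 3 or greater rated possibly, probably or definitely related.
2. In the second sentence, replace grade 3 with grade 3 or greater for the second event. Add no attribution limit, so that the notification and accrual stop remain at least as broad as they are now.

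With the first change, all six label pairs in the table reach the count of 2. The cost is two wording changes in one section, with no new data, visits or patients.
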